Appendix 7.	Pregnancy Precautions, Definition for Female of Childbearing Potential, and Contraceptive Requirements.....	129
Appendix 8.	Prior and Concomitant Medications For Subjects in Sentinel Cohort 1 and Sentinel Cohort 1 Subjects Who Go on to Part 2: bicitegravir GS-9131 + BIC + DRV + RTV	131

LIST OF IN-TEXT TABLES

Table 1.	Estimated Exposure Margins for GS-9131 and GS-9148 in Female Animals Relative to 180 mg GS-9131	23
Table 2.	Study GS-US-180-4149 Preliminary Plasma PK Data from Cohorts 1-5	26
Table 3.	Study GS-US-180-4149 Preliminary PBMC PK Data from Cohorts 1-5.....	28
Table 4.	Study GS-US-180-0104 Multiple Dose PK Data	30
Table 5.	Study GS-US-442-4148 Preliminary PK Data	31
Table 6.	Prior and Concomitant Medications*	56

LIST OF IN-TEXT FIGURES

Figure 1.	Study GS-US-442-4148: Changes in Viral Load by Subject and Failing ARV Regimen in the Sentinel Cohort.....	32
Figure 2.	Study Schema – Cohort 1	46
Figure 3.	Study Schema – Cohort 2	47
Figure 4.	Suboptimal Virologic Response Schema.....	70
Figure 5.	Virologic Rebound Schema.....	72

PROTOCOL SYNOPSIS

Gilead Sciences, Inc.
[name]
[name]

Study Title: A Phase 2 Study to Evaluate the Efficacy of GS-9131 Functional Monotherapy in HIV-1-Infected Adults Failing a Nucleos(t)ide Reverse Transcriptase Inhibitor-Containing Regimen with Nucleos(t)ide Reverse Transcriptase Inhibitor Resistant Virus

IND Number: 132376

EudraCT Number: Not Applicable

Clinical Trials.gov Identifier: NCT03472324

Study Centers Planned: Uganda, Zimbabwe

Objectives: The primary objective of this study is as follows:

- To evaluate the short-term antiviral potency of GS-9131 functional monotherapy compared to placebo-to-match (PTM) GS-9131, each administered once daily with the existing failing antiretroviral (ARV) regimen, as demonstrated by the proportion of subjects achieving HIV-1 RNA $> 0.5 \log_{10}$ decreases from baseline through up to 14 days of therapy.

The secondary objectives of this study are as follows:

Part 1

- To evaluate the efficacy of GS-9131 functional monotherapy as determined by the change from baseline in \log_{10} HIV-1 RNA at Day 11 (Sentinel Cohort 1) or Day 15 (Sentinel Cohort 2 and Randomized Cohort).

Part 2

- To evaluate the safety and efficacy of a regimen containing GS-9131 (60 mg) + bictegravir (BIC) + darunavir (DRV) + ritonavir (RTV) through 24 weeks of treatment in subjects from Sentinel Cohort 1 who switched from a failing regimen.
- To evaluate the safety and efficacy of a regimen containing GS-9131 + bictegravir (BIC) + tenofovir alafenamide (TAF) through 24 weeks of treatment in subjects from Sentinel Cohort 2 and Randomized Cohort who switched from a failing regimen.

- To characterize the pharmacokinetics (PK) of GS-9131 in treatment-experienced patients.
- To evaluate the number of subjects with treatment-emergent nucleos(t)ide reverse transcriptase inhibitor (NRTI), protease inhibitor (PI), and integrase strand-transfer inhibitor (INSTI) mutations at the time of virologic failure.

Study Design:

Part 1: GS-9131 Functional Monotherapy

The study will consist of 3 cohorts - Two Sentinel Cohorts and one Randomized Cohort.

The Sentinel Cohort 1 will enroll 10 TE viremic HIV-1 subjects to receive open-label GS-9131 60 mg for 10 days in addition to their current failing ARV regimen.

Sentinel Cohort 2 will enroll up to 10 TE viremic HIV-1 subjects to receive open-label GS-9131 180 mg for 14 days in addition to their current failing ARV regimen.

Sentinel cohort subjects who meet criteria for Part 2, will transition to Part 2 and not participate in the randomized portion of this study.

The Sentinel Cohorts will be followed by a Randomized Cohort that is a double-blind comparison of the addition of GS-9131 (up to 180 mg), or PTM to the current failing ARV regimen in viremic HIV-1 positive adults. Randomization and dosing into the Randomized Cohort will begin after review of the clinical data in the second Sentinel Cohort.

In the Randomized Cohort, up to 48 subjects failing their current ARV regimen will be randomized 1:1:1:1 to GS-9131 (up to three active dose levels, up to 180 mg), or PTM. The GS-9131 dose for Treatment Arms A-C will be determined following review of the safety, activity and available PK data from Sentinel Cohort 2. GS-9131 will be added to their failing regimen for 14 days as follows:

Treatment Arms A-C: GS-9131 once daily + current failing antiretroviral therapy (ART) regimen (n=12 per Treatment Arm)

Treatment Arm D: PTM + current failing ART regimen (n=12)

Randomization will be stratified by HIV-1 RNA level ($\leq 100,000$ copies/mL and $> 100,000$ copies/mL) at screening.

Study medication will be administered by directly observed therapy (DOT).

**Part 2: GS-9131 + BIC + DRV + RTV or GS-9131 + BIC + TAF
Combination Therapy**

GS-9131(60 mg) + BIC (30 mg) + DRV(800 mg) + RTV(100 mg)
Regimen (Sentinel Cohort 1)

Subjects who successfully complete all study doses in Sentinel Cohort 1 and show a reduction in plasma HIV RNA $> 0.5 \log_{10}$ from their pre-GS-9131 baseline following functional monotherapy will discontinue their current failing regimen and start an optimized regimen consisting of GS-9131 (60 mg) + BIC + DRV + RTV for at least 24 weeks.

GS-9131(up to 180 mg) + BIC (75 mg) + TAF (25 mg) (Sentinel Cohort 2 and Randomized Cohort)

Subjects who successfully complete all study doses in Sentinel Cohort 2 and Randomized Cohort (A-C), and show a reduction in plasma HIV RNA $> 0.5 \log_{10}$ from their pre-GS-9131 baseline during functional monotherapy will discontinue their current failing regimen and start an optimized regimen consisting of GS-9131 + BIC + TAF for at least 24 weeks. All Subjects randomized to the placebo arm (Cohort D) will discontinue their current failing regimen and start a regimen consisting of GS-9131(180 mg) + BIC + TAF for at least 24 weeks.

CCI

An Independent Data Monitoring Committee (IDMC) will review the progress, efficacy, and safety data while the study is ongoing. The committee will convene after all subjects in the randomized cohort have completed Part 1 and after approximately 50% of subjects in Part 2 have completed Week 12 of Part 2 of the study.

Number of Subjects
Planned:

Approximately 68 female subjects will be enrolled in this study. Replacement subjects may be enrolled for subjects who do not complete all procedures in the functional monotherapy treatment for reasons other than discontinuation due to treatment related adverse events (AEs).

Target Population:	HIV-1 infected adult females ≥ 18 years of age failing a 2 nucleoside reverse transcriptase inhibitor (NRTI) + non-nucleoside reverse transcriptase inhibitor (NNRTI) containing treatment regimen with plasma HIV-1 RNA level ≥ 500 copies/mL, evidence of K65R or 3 or more thymidine analog mutations (TAMs) or Q151M, and at least one documented primary resistance associated mutation to NNRTIs.
Duration of Treatment:	Part 1 Sentinel Cohort 1: 10 days. Part 1 Sentinel Cohort 2 and Randomized Cohort : 14 days each Part 2: At least 24 weeks
Diagnosis and Main Eligibility Criteria:	
HIV-1 infected subjects who meet the following criteria:
 
• Non-pregnant/non-lactating females, ≥ 18 years of age at Screening. Females of childbearing potential (as defined in Appendix 7) must have a negative serum pregnancy test at Screening and Day 1.• Subjects of childbearing potential who engage in heterosexual intercourse must agree to use protocol-specified method(s) of contraception as described in Appendix 7.• Estimated glomerular filtration rate (eGFR) (Cockcroft-Gault equation) ≥ 70 mL/min• Currently taking a failing ARV regimen that contains an NRTI• HIV-1 RNA ≥ 500 copies/mL at Screening• CD4 > 100 cells/μL at Screening• Have a screening genotype showing at least the following resistance mutation profile (a local genotype at the Screening visit is acceptable for enrollment upon review by the Sponsor):
— K65R or— at least 3 TAMs; TAMs are defined as: M41L, D67N, K70R, L210W, T215F/Y, or K219Q/E/N/R in reverse transcriptase (RT) or— Q151M— and at least one primary resistance mutation to an NNRTI• No prior or current ARV regimens containing integrase inhibitor (INSTI) or protease inhibitor (PI)• No evidence of chronic viral hepatitis B or C infection. Note: Subjects with positive hepatitis C virus (HCV) antibody and without detectable HCV RNA are permitted to enroll. 
No evidence of active AIDS-related opportunistic infection, including tuberculosis.

Study Procedures/
Frequency:

At Screening, laboratory analyses (hematology, chemistry, urinalysis, and serum pregnancy test [for females of childbearing potential]), HIV-1 RNA, cluster determinant 4 (CD4) cell count, vital signs, electrocardiogram (ECG), complete physical examination, and eGFR will be performed. HIV-1 protease, and reverse transcriptase genotype/phenotype, and hepatitis B virus (HBV) and HCV serologies will be analyzed.

Part 1:

Sentinel Cohort 1 (GS-9131 60 mg plus Current Failing Regimen)

Following Screening and Day 1 (baseline) visits, subjects will be required to visit the clinic daily on Days 2-11. All study medication will be delivered by DOT on Days 1-10.

Laboratory analyses (hematology, chemistry, and urinalysis) will be performed at Day 1 (baseline), Day 7, and Day 11. A fasting metabolic profile will be performed on Day 1. Urine and serum pregnancy test (females of childbearing potential only) will be done at Screening and Day 1 and a urine pregnancy test on Day 11; positive urine pregnancy test on Day 11 will be confirmed with a serum pregnancy test. CD4 T cell count will be performed at Screening, Day 1 (baseline), and Day 11. A plasma sample for phenotypic and genotypic testing of HIV-1 resistance will be collected at Screening, Day 1, and Day 11. A complete physical examination will be performed at Screening, Day 1 (baseline), and Day 11. Symptom driven physical exam will be performed on Day 2 and Day 7. ECGs will be performed at Screening, Day 1, and Day 11.

On Day 10, all subjects will participate in a PK evaluation.

Samples for HIV-1 RNA will be collected at Screening, Day 1 (baseline), and Days 2, 3, 7, 10, and 11.

Assessments of AEs and concomitant medications will be performed at each visit.

Sentinel Cohort 2 (GS-9131 180 mg plus Current Failing Regimen) and Randomized Cohort (GS-9131 or PTM plus Current Failing Regimen)

Following Screening and Day 1 (baseline) visits, all study medication will be delivered by DOT on Days 1-14.

Laboratory analyses (hematology, chemistry, and urinalysis) will be performed at Days 1 (baseline), 3, 5, 7, 10, 14, and 15. A fasting metabolic profile will be performed on Day 1. Urine and serum

pregnancy test (females of childbearing potential only) will be done at Screening and Day 1 and a urine pregnancy test on Days 10 and 14; positive urine pregnancy test will be confirmed with a serum pregnancy test. CD4 T cell count will be performed at Screening and Days 1 (baseline), 10, 14, and 15. A plasma sample for phenotypic and genotypic testing of HIV-1 resistance will be collected at Screening and Days 1, 10, 14, and 15. A whole blood sample for genotypic testing of HIV-1 resistance will be collected at Day 1. A complete physical examination will be performed at Screening and Days 1 (baseline), and 14. Symptom driven physical exam will be performed on Days 2 and 7. ECGs will be performed at Screening, Day 1 and Day 15.

On Day 14, all subjects will participate in a PK evaluation.

Samples for HIV-1 RNA will be collected at Screening and Days 1 (baseline), 3, 7, 10, 14, and 15.

Assessments of AEs and concomitant medications will be performed at each visit.

Part 2:

GS-9131 + BIC + DRV + RTV Regimen (Sentinel Cohort 1)

Subjects in the Sentinel Cohort 1 who had a $> 0.5 \log_{10}$ decline in HIV-1 RNA in Part 1 will discontinue their current failing regimen and begin treatment with GS-9131 + BIC + DRV + RTV once daily for 24 weeks. Subjects who had a $\leq 0.5 \log_{10}$ decline in HIV-1 RNA are not eligible to continue onto Part 2 and will be discontinued from the study.

At their Day 1 visit for Part 2, AEs, concomitant medications, drug accountability, vital signs, physical examinations, HIV-1 RNA, estimated GFR, hematology, chemistry, CD4 cell count, and urinalysis will be performed.

All subjects will be required to visit the clinic on Day 1, and Weeks 1, 2, 4, 8, 12, 18, and 24. At each visit, AEs, concomitant medications, drug accountability, hematology, chemistry, HIV-1 RNA, CD4 cell count, vital signs, and estimated GFR will be evaluated. A fasting metabolic profile will be performed on Day 1, Week 12 and 24 visits. A complete physical examination will be done at Day 1, Week 12 and 24 visits. A symptom directed physical examination will be done at all other visits. Urinalysis will be performed at Day 1, and Week 4, 12, and 24 visits. Urine pregnancy test (females of childbearing potential only) will be done on Day 1, and Weeks 4, 8, 12, 18, and 24; positive urine pregnancy test will be confirmed with a serum pregnancy test.

CCI [REDACTED]

CCI [REDACTED]

GS-9131 + BIC + TAF (Sentinel Cohort 2 and Randomized Cohort)

Subjects in the Sentinel Cohort 2 or Randomized Cohort (A-C) who had a $> 0.5 \log_{10}$ decline in HIV-1 RNA in Part 1 will discontinue their current failing regimen and begin treatment with GS-9131 + BIC + TAF once daily for 24 weeks. Subjects who had a $\leq 0.5 \log_{10}$ decline in HIV-1 RNA are not eligible to continue onto Part 2 and will be discontinued from the study. Subjects in Randomized Cohort D will begin treatment with GS-9131(180 mg) + BIC (75 mg) + TAF (25 mg) once daily for 24 weeks after successful completion of Part 1.

At their Day 1 visit for Part 2, AEs, concomitant medications, drug accountability, vital signs, physical examinations, HIV-1 RNA, estimated GFR, hematology, chemistry, CD4 cell count, and urinalysis will be performed.

All subjects will be required to visit the clinic on Day 1, and Weeks 1, 2, 4, 8, 12, 18, and 24. At each visit, AEs, concomitant medications, drug accountability, hematology, chemistry, HIV-1 RNA, CD4 cell count, vital signs, and estimated GFR will be evaluated. A fasting metabolic profile will be performed on Day 1, Week 12 and 24 visits. A complete physical examination will be done at Day 1, Week 12 and 24 visits. A symptom directed physical examination will be done at all other visits. Urinalysis will be performed at Day 1, and Week 4, 12, and 24 visits. Urine pregnancy test (females of childbearing potential only) will be done on Day 1, and Weeks 4, 8, 12, 18, and 24; positive urine pregnancy test will be confirmed with a serum pregnancy test.

CCI [REDACTED]

CCI [REDACTED]

CCI [REDACTED]

Protocol-Specific Stopping Rules

By Subject: Study drug dosing for a subject will be discontinued if that subject experiences a Grade 3 or Grade 4 treatment-emergent adverse event (AE) or confirmed laboratory abnormality judged by the study investigator to be possibly related to study drug, or any serious adverse event (SAE) considered to be possibly related to study drug.

By Sentinel Cohort: Study drug dosing for the Sentinel Cohorts will be discontinued if any of the following criteria is met:

- 2 or more subjects experiencing Grade 3 or Grade 4 treatment-emergent AEs judged by the study investigator to be possibly related to study drug, or
- 2 or more subjects experiencing confirmed Grade 3 or Grade 4 laboratory abnormalities, or
- 2 or more subjects experiencing any SAE that is considered to be possibly related to study drug.

For the Randomized Cohort and Part 2: If 2 or more subjects in the Randomized Cohort who are subsequently assigned to treatment cohorts in Part 2 experience a Grade 3 or 4 treatment-emergent AE leading to study drug discontinuation or an SAE judged by the study investigator to be possibly related to study drug, the IDMC will be convened to review all preliminary safety data generated in subjects dosed to date.

Subjects will be followed as clinically indicated until the treatment-emergent AE or laboratory abnormality returns to baseline or is otherwise explained, whichever occurs first. Grade 3 and 4 laboratory abnormalities that are not confirmed by repeat testing will be managed according to the clinic's practice; a decision to reinitiate dosing may be made by Gilead in consultation with the investigator and after a safety review.

Test Product, Dose, and Mode of Administration:	Part 1 Sentinel Cohort 1: GS-9131 (60 mg) Part 1 Sentinel Cohort 2 and Randomized Cohort: GS-9131 (up to 180 mg) and PTM
--	---

Part 2:

Sentinel Cohort 1: GS-9131 (60 mg) + BIC (30 mg) + DRV (800 mg) + RTV (100 mg)

Sentinel Cohort 2 and Randomized Cohort: GS-9131 (doses up to 180 mg) + BIC (75 mg) + TAF (25 mg)

Reference Therapy, Dose, and Mode of Administration:

Part 1: Current ARVs

Part 2: None

Criteria for Evaluation:

Efficacy:

The primary endpoint is:

- The proportion of subjects with plasma HIV-1 RNA decreases from baseline exceeding 0.5 log₁₀ (copies/mL) at Day 15 in the Randomized Cohort.

The secondary endpoints are:

- The change from baseline in plasma log₁₀ HIV-1 RNA (copies/mL) at Day 11 for Sentinel Cohort 1 and Day 15 for Sentinel Cohort 2 and the Randomized Cohort in Part 1.
- The proportion of subjects with plasma HIV-1 RNA < 50 copies/mL at Week 24 as defined by the US FDA Snapshot algorithm. The number of subjects with treatment-emergent NRTI, PI, or INSTI mutations at the time of virologic failure.

Safety:

The safety and tolerability of GS-9131 in subjects who failed an NRTI-containing regimen with NRTI-resistant virus through Day 15, assessed by clinical exams, laboratory parameters and AE reporting.

The safety and tolerability of switching to the regimen of GS-9131 + BIC + DRV + RTV or GS-9131 + BIC + TAF in subjects who failed an NRTI-containing regimen with NRTI-resistant virus through Week 24, assessed by clinical exams, laboratory parameters and AE reporting.

Pharmacokinetics:

Sentinel Cohort 1 (60 mg): Intensive plasma and PBMC samples will be collected in all subjects on Day 10. Serial blood samples for plasma and peripheral blood mononuclear cell (PBMC) PK assessments will be collected at the following timepoints:

Plasma collection on Day 10: Predose (< 5 minutes prior to dosing), 0.5, 1, 1.5, 2, 3, 4, 6, 8, and 24 hours post dose.

PBMC collection on Day 10: Predose (< 5 minutes prior to dosing), 1, 2, 6, and 24 hours post dose.

Sentinel Cohort 2 (180 mg) and Randomized Cohort: Intensive plasma and PBMC PK samples will be collected in all subjects on Day 14. Serial blood samples for plasma and peripheral blood mononuclear cell (PBMC) PK assessments will be collected at the following timepoints:

Plasma collection on Day 14: Predose (< 5 minutes prior to dosing), 0.5, 1, 1.5, 2, 3, 4, 6, 8, and 24 hours post dose.

PBMC collection on Day 14: Predose (< 5 minutes prior to dosing), 1, 2, 6, and 24 hours post dose

The PK of GS-9131 and its metabolite, GS-9148, in plasma, will be evaluated. The PK of GS-9148-diphosphate (DP) in PBMCs and the PK of other analytes may be explored.

CCI [REDACTED]

[REDACTED]

[REDACTED]

[REDACTED]

[REDACTED]

[REDACTED]

[REDACTED]

[REDACTED]

[REDACTED]

[REDACTED]

CCI

Statistical Methods:

For Part 1, the proportion of subjects with plasma HIV-1 RNA decreases from baseline exceeding $0.5 \log_{10}$ at Day 15 in the Randomized Cohort will be compared between each active GS-9131 treatment group and the placebo group using Fisher's exact test.

The change from baseline in plasma \log_{10} HIV-1 RNA (copies/mL) at Day 15 will be summarized by cohort and treatment group.

For Part 2, the proportion of subjects with plasma HIV-1 RNA < 50 copies/mL at Week 24 will be summarized by treatment group using the US FDA-defined Snapshot Algorithm and the missing = failure /excluded approaches for imputing missing HIV-1 RNA values. The 95% confidence interval (CI) of the proportion of subjects with HIV-1 RNA < 50 copies/mL at Week 24 will be calculated using the Clopper-Pearson Exact method. In addition, the change from Part 2 baseline (i.e., predose of an optimized regimen consisting GS-9131 in Part 2) in \log_{10} HIV-1 RNA and CD4 cell count at Week 24 will be summarized by treatment group using descriptive statistics. The 95% CI will be calculated.

Adverse event data including treatment-emergent AEs and SAEs will be summarized by system organ class (SOC) and preferred term (PT) using the Medical Dictionary for Regulatory Activities (MedDRA) by treatment group in each part and cohort.

Listings of individual subject vital signs, 12-lead ECG parameters, and laboratory results will be provided. Laboratory results and change from predose/baseline values for selected tests will be summarized at scheduled visits by treatment group in each part and cohort. The incidence of treatment-emergent laboratory abnormalities will be summarized by treatment group in each part and cohort as well.

For the sample size and power calculation for the Randomized Cohort in Part 1, assuming that 70% of subjects in each GS-9131 treatment group and 8.3% in the placebo group achieve $> 0.5 \log_{10}$ HIV-1 RNA decrease from baseline at Day 15, a sample size of 12 subjects per treatment group (48 in total) provides 85% power to detect the difference in the response rates between at least one GS-9131 treatment group and the placebo group with a Fisher's exact test to be done at a two-sided alpha level of 0.05.

This study will be conducted in accordance with the guidelines of Good Clinical Practice (GCP) including archiving of essential documents.

GLOSSARY OF ABBREVIATIONS AND DEFINITION OF TERMS

° C	degrees Celsius
° F	degrees Fahrenheit
AE	adverse event
AhR	aryl hydrocarbon receptor
AIDS	acquired immune deficiency syndrome
ALT	alanine aminotransferase
ART	antiretroviral therapy
ARV	Antiretroviral
AST	aspartate aminotransferase
AUC	area under the plasma/serum/peripheral blood mononuclear cell concentration versus time curve
BIC, B	Bictegravir
B/F/TAF	bictegravir/emtricitabine/tenofovir alafenamide
BUN	blood urea nitrogen
CBC	complete blood count
CFR	FDA code of federal regulations
CI	confidence interval
CK	creatine kinase
CL _{cr}	creatinine clearance
C _{max}	the maximum observed serum/plasma/peripheral blood mononuclear (PBMC) concentration of drug
CMH	Cochran-Mantel-Haenszel
C _{tau}	the observed drug concentration at the end of the dosing interval
COBI	cobicistat, Tybost®
CPK	creatine phosphokinase
CRO	contract (or clinical) research organization
CSR	clinical study report
CYP	cytochrome P450
DHHS	Department of Health and Human Services
DOT	Directly observed therapy
DNA	deoxyribonucleic acid
DP	Diphosphate
DRV	darunavir, Prezista®
DTG	dolutegravir, Tivicay®
ECG	Electrocardiogram
eCRF	electronic case report form(s)
eGFR	estimated glomerular filtration rate
EVG	elvitegravir, E
E/C/F/TAF	elvitegravir/cobicistat/emtricitabine/tenofovir alafenamide, Genvoya®

FAS	full analysis set
FDA	(United States) Food and Drug Administration
FDC	fixed dose combination
FSH	follicle stimulating hormone
F/TAF	emtricitabine/tenofovir alafenamide, Descovy®
FTC/TDF	emtricitabine/tenofovir disoproxil fumarate
GCP	Good Clinical Practice (Guidelines)
GD	gestation day
GSI, Gilead	Gilead Sciences, Inc.
HAART	highly active antiretroviral therapy
HBV	hepatitis B virus
HBcAb	hepatitis B core antibody
HBeAB	hepatitis B virus e-antibody
HBsAb	hepatitis B surface antibody
HBsAg	hepatitis B surface antigen
HCV	hepatitis C virus
HDPE	high-density polyethylene
hERG	human Ether-à-go-go-Related Gene
HIV	human immunodeficiency virus
HLGT	high-level group term
HLT	high-level term
IB	Investigator's Brochure
ICH	International Conference on Harmonisation
IDMC	Independent Data Monitoring Committee
IEC	Independent Ethics Committee
IMP, study drug	investigational medicinal products
INSTI	integrase strand-transfer inhibitor
INR	international normalized ratio
IRB	institutional review board
IUD	intrauterine device
IWRS	interactive web response system
KS	Kaposi's sarcoma
LAM	lactational amenorrhea method
LDL	low density lipoprotein
LLT	lower level term
LSM	least-squares mean
MedDRA	Medical Dictionary for Regulatory Activities
Mg	Milligram
Min	Inute
mtDNA	mitochondrial DNA

NNRTI	non-nucleoside reverse transcriptase inhibitor
NOAEL	no observed adverse effect level
NOEL	no observed effect level
NRTI	nucleoside/nucleotide reverse transcriptase inhibitor
N(t)RTI	nucleos(t)ide reverse transcriptase inhibitor
PAH	pulmonary arterial hypertension
PBMC	peripheral blood mononuclear cell
PI	protease inhibitor
PK	Pharmacokinetic
PP	per-protocol
PT	preferred term
PTM	placebo-to-match
PVE	Pharmacovigilance & Epidemiology
PXR	pregnane X receptor
QD	once daily
RNA	ribonucleic acid
RT	reverse transcriptase
RTV	ritonavir, Norvir [®]
SADR	serious adverse drug reaction
SAE	serious adverse event
SOC	system organ class
SOP	standard operating procedures
SUSAR	Suspected Unexpected Serious Adverse Reaction
TAF	tenofovir alafenamide
TAM	thymidine analogue mutations
TDF	tenofovir disoproxil fumarate, Viread [®]
TE	treatment experienced
TFV	Tenofovir
UGT1A1	uridine 5'-diphospho-glucuronosyltransferase
ULN	upper limit of the normal range
US	United States
USPI	United States prescribing information
WHO	World Health Organization

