1.9. Risk/Benefit Assessment for the Study

All patients with HIV-1 infection, including those with drug resistant viruses, benefit from receiving effective ART. The risks in the study patient population who are failing their current ARV regimen are considered to be low. Important risks will be appropriately managed by study inclusion/exclusion criteria, as well as close monitoring during the study.

All subjects will be monitored daily during the functional monotherapy period and at frequent intervals in Part 2 of the study. Monitoring will include clinical evaluation, safety laboratory tests, and HIV-1 RNA viral load. In addition, stopping criteria will be implemented on an individual and cohort basis and the study will be monitored by an independent data safety monitoring board as well as local ethics committees. Important risks will be appropriately managed by study inclusion/exclusion criteria, as well as close monitoring, including clinical evaluation, safety laboratory assessment, individual and by-cohort stopping rules, and HIV-1 RNA viral load monitoring during the study.

If a median of > 0.5 log decrease in HIV-1 RNA is observed following administration of GS-9131 180 mg in the second Sentinel Cohort, GS-9131 doses ≤ 180 mg may be evaluated in the Randomized Cohort.

The only significant effect identified in chronic animal studies with BIC was hepatobiliary toxicity in monkeys following 39 weeks of administration at a dose (1000 mg/kg/day) which produced plasma exposures to BIC that were 16-fold higher than those observed in patients at a 50 mg BIC dose. The effects were partially reversible after a 4-week period of non-exposure (recovery). No toxicity was observed at the mid-dose of BIC 200 mg/kg/day, which provided a margin of exposure 7-fold greater than the projected clinical exposure. Potential hepatobiliary toxicity is appropriately managed by study inclusion/exclusion criteria, close clinical and laboratory monitoring, as well as specific toxicity management guidance to investigators. As of 06 August 2018, 2740 subjects have been exposed to B/F/TAF in clinical trials with no evidence of hepatotoxicities. (Refer to BIC & TAF IB).

Consistent with other members of the INSTI class, BIC has been well-tolerated in clinical studies to date.

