8.5. Efficacy Analysis

8.5.1. Primary Analysis

The primary efficacy endpoint is the proportion of subjects with HIV-1 RNA decreases from baseline exceeding $0.5 \log_{10}$ copies/mL at Day 15 for Part 1, Randomized Cohort. Subjects who have missing HIV-1 RNA values at Day 15 will be considered as without an HIV-1 RNA decrease from baseline exceeding $0.5 \log_{10}$ copies/mL at Day 15. The difference between each of the GS-9131 treatment groups and the placebo group will be compared using a Fisher's exact test at a two-sided significant level of 0.05.

The null hypothesis is that there is no difference in proportion of subjects with HIV-1 RNA decreases exceeding $0.5 \log_{10}$ at Day 15 between each of the GS-9131 treatment groups and the placebo group; the alternative hypothesis is that there is a difference in the proportion of subjects with HIV-1 RNA decreases exceeding $0.5 \log_{10}$ copies/mL at Day 15 between each of the GS-9131 treatment groups and the placebo group.

The primary analysis of the efficacy will be based on FAS in Part 1.

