8.9. Sample Size

For the Randomized Cohort in Part 1, a total of 48 HIV-1 positive adults, randomized in a 1:1:1:1 ratio to 4 arms (3 dose levels of GS-9131 up to 180 mg, and placebo) achieves 85% power to detect a 61.7% difference in the proportion of subjects with HIV-1 RNA decreases from baseline exceeding $0.5 \log_{10}$ between at least one of the GS-9131 treatment arms and placebo arm at Day 21. For sample size and power computation, it is assumed that 70% of subjects in each GS-9131 arm achieved a reduction exceeding $0.5 \log_{10}$ HIV-1 RNA while 8.3% of subjects in the placebo arm achieved such a reduction (based on internal Viread Study 907), and a Fisher's exact test at a two-sided significance level of 0.05 was conducted.

Sample size and power calculations were made using nQuery Advisor 6.0.

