### **1.3. Sample Size and Power**

For the sample size and power calculation for the randomized cohort in Part 1, assuming that 70% of subjects in each GS-9131 treatment group and 8.3% in the placebo group achieve  $> 0.5 \log_{10}$  HIV-1 RNA decrease from baseline at Day 15, a sample size of 12 subjects per treatment group (48 in total) provides 85% power to detect the difference in the response rates between at least one GS-9131 treatment group and placebo group with a Fisher's exact test to be done at a two-sided alpha level of 0.05.

Sample size and power calculations were made using the statistical software package nQuery Advisor (Version 6.0).

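### The 85% power stated for at least one GS-9131 dose versus placebo is the power of a single dose-versus-placebo test; the event it names has about 98% power under the plan's own assumptions.

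*Protocol*

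**What the plan says.** The synopsis (Statistical Methods) sets the premise, "assuming that 70% of subjects in each GS-9131 treatment group and 8.3% in the placebo group achieve" the required fall in HIV-1 RNA at Day 15. It then claims that a cohort of 48, with 12 people in every arm, "provides 85% power to detect the difference in the response rates between at least one GS-9131 treatment group and the placebo group". The calculation assumes Fisher's exact test, two-sided, at 0.05.

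Protocol Section 8.9 gives the same calculation: the trial "achieves 85% power to detect a 61.7% difference in the proportion of subjects with HIV-1 RNA decreases" beyond the threshold. That section describes the comparison as one made "between at least one of the GS-9131 treatment arms and placebo arm at Day 21". SAP Section 1.3 repeats the claim, at Day 15: the planned cohort "provides 85% power to detect the difference in the response rates between at least one GS-9131 treatment group and placebo group". No other power figure appears in either document.

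The analysis is per dose. Protocol Section 8.5.1 has this sentence: "The difference between each of the GS-9131 treatment groups and the placebo group will be compared using a Fisher's exact test". Every such comparison uses the 0.05 level, two-sided, and the null and alternative hypotheses are framed dose by dose. The number of active arms is not fixed. The synopsis allows up to three, and protocol Section 3.3 leaves the doses and number of cohorts to the Sentinel Cohort 2 data.

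**The concern.** Three active arms give three chances of a significant result. If each dose is assumed to have 70% response, the chance that at least one comparison succeeds must exceed the chance that a particular one does. A single figure of 85% can describe one of these events but not both. The text attaches it to the first, while the hypotheses in Section 8.5.1 concern the second.

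What is at stake is interpretation. To judge a non-significant arm, a reader needs the power of that arm's own comparison. Taken literally, the text gives only the power for the best of several comparisons, and the reader would conclude that each single comparison has less than 85%.

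Day 21 in Section 8.9 is a further slip in the same sentence. The primary endpoint is at Day 15 in the synopsis and in protocol Sections 3.1, 8.1.2 and 8.5.1. The Part 1 schedule for this cohort in protocol Appendix 3 ends at Day 15.

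**Working it through.** **Inputs.** Response 0.70 in each active arm and 0.083 on placebo; 12 per arm; Fisher's exact test, two-sided 0.05 (synopsis, protocol 8.9, SAP 1.3). The difference is 0.70 − 0.083 = 0.617, which agrees with the 61.7% in Section 8.9. Allocation is 1:1:1:1, so the active arms share one placebo arm.

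**Method.** Let c be the number of placebo responders, with c ~ Binomial(12, 0.083). For each c, find the smallest number of active responders t that gives Fisher p ≤ 0.05 in the direction of benefit. Let g(c) = P(T ≥ t), with T ~ Binomial(12, 0.70). Given c, the active arms are independent, so:

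- one dose versus placebo: Σ P(c)·g(c)
- at least one of k doses: Σ P(c)·[1 − (1 − g(c))^k]

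| c | P(c) | t needed | g(c) | P(c)·g(c) | P(c)·[1 − (1 − g(c))³] |
|---|---|---|---|---|---|
| 0 | 0.3535 | 5 | 0.9905 | 0.3502 | 0.3535 |
| 1 | 0.3840 | 7 | 0.8822 | 0.3387 | 0.3834 |
| 2 | 0.1912 | 8 | 0.7237 | 0.1383 | 0.1871 |
| 3 | 0.0577 | 9 | 0.4925 | 0.0284 | 0.0501 |
| 4 | 0.0117 | 10 | 0.2528 | 0.0030 | 0.0068 |
| 5 | 0.0017 | 11 | 0.0850 | 0.0001 | 0.0004 |
| 6 or more | 0.0002 | 12 or none | ≤ 0.0138 | 0.0000 | 0.0000 |
| Sum, unrounded terms | | | | **0.859** | **0.981** |

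**Plan's figure.** One dose against placebo gives 85.9%, or 85.8% with the placebo rate taken as 1/12. This reproduces the stated 85%.

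**Event named in the text.** At least one of three doses gives 98.1%. With k = 2 the same sum gives 95.7%, and with k = 1 it returns to 85.9%. A simulation of 400,000 trials gave 85.9% for one dose and 98.1% for at least one of three. Treating the three comparisons as independent would give 1 − (1 − 0.859)³ = 99.7%; the shared placebo arm lowers this to 98.1%.

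**Gap.** 98.1 − 85 = 13.1 percentage points, with the stated figure too low.

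**Could another reading rescue the label?** If one dose had 70% response and the other two matched placebo, power for at least one would be 85.9%. The text, however, assumes 70% in each active group. A Bonferroni level of 0.05/3 gives 93.2% for at least one of three and about 73% for one dose; neither is 85%, and no adjustment is planned.

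**The case against.** The best case for the plan is that the statement is conservative. A design with 98.1% power for at least one dose does have at least 85%, and it would keep 93.2% under Bonferroni. The printed number is also, within a point, the pairwise power that Section 8.5.1 needs. The SAP reports that the study was stopped (Section 2.4) and that the randomized cohort produced no efficacy data (Section 6), so nothing reported depends on it. All of this stands, and it makes the point minor. The label is still wrong: the figure does not follow from the stated inputs for the event it names.

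Stronger readings are tempting, but the documents do not support them:

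- **The design lacks the power claimed.** The reverse is true: 12 per arm more than meets the stated aim.
- **Power to show that all doses work is overstated.** At 70% in each arm, the chance that all three comparisons are significant is 68.7%. No section claims power for that event.
- **The go rule undercuts the 70% assumption.** Protocol Section 1.9 begins: "If a median of > 0.5 log decrease in HIV-1 RNA is observed following administration of GS-9131 180 mg in the second Sentinel Cohort", and then says that doses up to 180 mg may be evaluated. A reader might infer that the trial proceeds at 50% response, where per-dose power is only 47.5%. That rule is permissive and concerns observed results at 180 mg. SAP Section 2.4 gives the pre-defined criterion, under which the study stops if half or more of Sentinel Cohort 2 fail to respond. Exactly 50% response is therefore a stop. A minimum gate in about 10 subjects is also not a planning assumption.
- **The 60 mg result (2 of 11) shows the premise is wrong.** That was 10 days of treatment assessed at Day 11. Protocol Section 1.7 suggests that dose and duration may have been too low, and no section assigns 60 mg to a randomized arm.

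**Conclusion.** The point holds as a labelling error. The 85% in the synopsis, protocol Section 8.9 and SAP Section 1.3 is the power of one dose-versus-placebo Fisher test (85.9%). For at least one dose it should read about 98% with three active arms, or about 96% with two. Per-dose power is not identified anywhere, although it is what the analysis uses. Day 21 in Section 8.9 contradicts the Day 15 endpoint.

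The figures rest on the plan's own inputs: 70% in every active arm, 8.3% on placebo, 12 analysed per arm, a shared placebo arm and no multiplicity adjustment. The 98% applies only if three active arms open.

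Severity is minor. The error is conservative; the sample size, test and significance level are unaffected, and so is the final analysis.

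**What to change.** In the synopsis, protocol Section 8.9 and SAP Section 1.3, replace the power statement with: 12 subjects per arm give about 86% power for each GS-9131 dose-versus-placebo comparison at 70% versus 8.3% (Fisher's exact test, two-sided 0.05), and about 98% power for at least one dose if three active arms are opened. In Section 8.9, change Day 21 to Day 15.

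The cost is wording only, with no extra subjects and no change of test or significance level. If the SAP is already final, its Section 1 provides for recording the change in the clinical study report.
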